## Missing data methodology

A forced response was used to avoid participants skipping questions to prevent missing data.

A set of rules were agreed with how to deal with the possibility than one survey was completed on behalf of more than one team e.g., the Routinely Admitting Team (RAT) and Non-Routinely Admitting Team (N-RAT) in the same NHS Trust, or more than one response was submitted for the same team.

Participants were asked to complete 2 separate surveys if they were responsible for more than one team. If only one survey was completed the researcher would confirm that the person completing the survey was the most appropriate person for both teams and ask if the responses would be

the same or different for both teams. If the person was not the most appropriate person, the researcher would request the survey be forwarded to the most appropriate person for the other team. If the person confirmed they were the most appropriate person and that their responses would be the same for both team the researcher would impute the missing data for the second team and record as two responses.

The potential for more than one response to be submitted for a hospital team had been minimised by only sending the link to the named person. However, there was the possibility than the role of SLT Clinical Lead may be shared within a team.

Firstly, only completed screens were to be included. Secondly the researcher would confirm the person completing the survey was the correct person to do so. Finally, the first submission would be included.

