### **Survey administration**

The electronic survey was created using Qualtrics survey software and responses were automatically captured on the Qualtrics platform. Completed survey responses were exported from Qualtrics to SPSS software for statistical analysis.

The survey was distributed on 2/9/2020. The closing date for the survey was 2/10/2020. The hyperlink remained active for a few days after the closing date to allow for any late responders due to the COVID pandemic.

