## **Statistical analyses**

Only completed surveys will be analysed. The survey data will be analysed using descriptive and inferential statistics. Descriptive statistics will include analysis of categorical and continuous data. Descriptive statistics of categorical variables will be frequency analysis i.e., percentage of the different categories within each variable. For example, proportion of Hospital Teams that are Routinely Admitting Teams and Non-Routinely Admitting Acute Teams. Categorical data will be visualised with bar and pie charts. The evaluation method for continuous data (incidence of pneumonia) will be mean and standard deviation to evaluate the dispersion of pneumonia incidence across the hospital teams and visualised using histograms.

Inferential statistics (linear regression analysis) will be used to test the hypotheses and explore if there is an association between the dependent variable (incidence of stroke-associated pneumonia) and independent binary variables: 1. Hospital Teams that use Water only dysphagia screening protocols (DSP) versus Hospital Teams that use water and other consistencies DSPs, 2. Hospital teams that use written guidelines for the first specialist clinical bedside swallow assessment versus Hospital teams that do not use written guidelines for the first specialist swallow assessment, 3. Hospital Teams that insert Nasogastric Tubes (NGTs) overnight have increased risk of SAP compared to Hospital Teams that do not insert NGTs overnight and 4. Hospital Teams with a written oral care protocol versus those do not have a written oral care protocol. Linear regression analysis will be visualised using Model Summary tables with Coefficients and 95% Confidence Intervals.

The proposed analysis for each variable is given in Table 1.

Table 1 – Proposed analysis for each variable

Variable	Data Source (s)	Values	Type of variable	Analysis approach	Methods for summarising data
Hospital Team	Survey Question #3 Please type the name of your hospital and select from the drop-down menu. SSNAP 2019 Team Centred 72-hour cohort data	1 = Routinely Admitting Team 2 = Non-Routinely Admitting Team	Categorical – Nominal - dichotomous	Descriptive statistics (frequencies) - Proportion of completed surveys for Routinely Admitting Team and Non-Routinely Admitting Acute Teams by SCN Region	Table

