## Method for analysing the data for incidence of stroke-associated pneumonia

Stroke-associated pneumonia (SAP) will be defined as the administration of antibiotics for a new clinical diagnosis of pneumonia in the first 7 days after admission as determined by the treating physician. SSNAP Patient Centred Post 72-hour quarterly data for Antibiotics for newly acquired pneumonia in the first 7 days from clock start will be used to calculate an annual 2019 pneumonia percentage for each team to measure the dispersion of the of pneumonia incidence across the teams.

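### One survey can be recorded as two responses for teams in the same NHS Trust, but the planned regressions make no allowance for Trust, so positively correlated pairs would make the 95% intervals too narrow

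*SAP*

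**What the plan says.** Missing data methodology sets rules for one survey covering more than one team, and gives as its example "the Routinely Admitting Team (RAT) and Non-Routinely Admitting Team (N-RAT) in the same NHS Trust". The default is separate returns: "Participants were asked to complete 2 separate surveys if they were responsible for more than one team". If only one survey arrives, the researcher checks that the respondent is the right person for both teams and asks whether the answers would be the same. If both are confirmed, "the researcher would impute the missing data for the second team and record as two responses".

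Only the survey answers are carried across. The outcome stays specific to the team, because the registry data "will be used to calculate an annual 2019 pneumonia percentage for each team" (Method for analysing the data for incidence of stroke-associated pneumonia).

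Statistical analyses tests four binary team practices by linear regression on pneumonia incidence: "Linear regression analysis will be visualised using Model Summary tables with Coefficients and 95% Confidence Intervals". It mentions no Trust term, clustered standard error or random effect. Team type and region enter Table 1 only as a descriptive count ("Proportion of completed surveys for Routinely Admitting Team and Non-Routinely Admitting Acute Teams by SCN Region"). The two examples under Sensitivity analysis, regional response and Covid-period data, do not concern Trust.

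**The concern.** Two rows created from one survey share every exposure value and may share a Trust. Ordinary standard errors treat their residuals as unrelated. The SAP foresees such pairs and writes a rule for them, but gives no reason why their pneumonia percentages should be independent once the practice variable is accounted for. Teams in one Trust may well have features in common that the model does not contain.

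The four coefficients and their intervals are how the plan tests its hypotheses. If same-Trust outcomes are positively correlated, pairs with identical answers carry less information than their row count suggests, and a stated 95% interval covers less often than 95%. A reader cannot judge by how much unless the number of shared-answer records is reported.

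**Working it through.** The SAP has no figure of its own to reproduce: it gives no sample size calculation, standard deviation, within-Trust correlation or count of same-Trust pairs. The only fixed number is the ceiling of 166 teams (Sampling plan). The rest is assumed: 120 responding teams, 3 to 24 pairs, a same-Trust residual correlation ρ from −0.3 to 0.5, and the exposure split.

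**Formula.** Let the exposure groups have n1 and n0 teams. Let f1 and f0 be the shares of each group's rows that sit in same-answer pairs, and D the number of pairs whose two teams gave different answers. Then

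Var(b) = s²[(1 + f1ρ)/n1 + (1 + f0ρ)/n0 − 2Dρ/(n1·n0)].

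Ordinary regression uses approximately s²(1/n1 + 1/n0). With R the ratio of the true to the ordinary standard error, coverage is about 2Φ(1.96/R) − 1.

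**Same answers, pairs spread evenly, 50/50 split.** Here R = √(1 + fρ), with f = 2 × pairs/120. At ρ = 0.5:

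| Pairs | f | R | Coverage, formula | Coverage, simulation |
|---|---|---|---|---|
| 6 | 0.10 | √1.05 = 1.025 | 94.4% | 94.5% |
| 12 | 0.20 | √1.10 = 1.049 | 93.8% | 93.9% |
| 24 | 0.40 | √1.20 = 1.095 | 92.6% | 92.6% |

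The simulation used 200,000 runs per case (Monte Carlo error about 0.1 points). At ρ = 0.2 it gave 94.8%, 94.7%, 94.6% and 94.0% for 3, 6, 12 and 24 pairs. If all 166 teams respond, 24 pairs at ρ = 0.5 give 93.3%.

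**Same answers, pairs concentrated in a small group.** Take an 80/20 split (n1 = 24, n0 = 96) with 10 pairs all in the smaller group, so f1 = 20/24 = 0.833 and f0 = 0. At ρ = 0.5:

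- true variance factor: 1.4167/24 + 1/96 = 0.0694
- ordinary factor: 1/24 + 1/96 = 0.0521
- R = √(0.0694/0.0521) = √1.333 = 1.155
- coverage: 2Φ(1.96/1.155) − 1 = about 91%

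**Different answers.** These pairs can arise from the default of two separate surveys, not from the copying rule. At a 50/50 split with n1 = n0 = 60, R = √(1 − Dρ/60). With D = 12 and ρ = 0.5, R = √0.90 = 0.949 and coverage is 96.1%, so the interval is too wide.

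**Negative correlation.** Same-answer pairs at ρ = −0.3 give R = √(1 − 0.20 × 0.3) = √0.94 = 0.970 with 12 pairs, and coverage of 95.7%. The SAP gives no reason to expect this.

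**Bias.** Each row keeps its own team's percentage and an exposure that the respondent has confirmed. Correlation between rows alters the variance of the coefficient, not its expectation.

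**The case against.** The two-row rule is defensible in itself. The unit of analysis is the hospital team, and a respondent who confirms common practice supplies two true exposure values. A reader might infer from the word impute that data are invented, or that a record is duplicated and the coefficients distorted. The SAP does not support that: the copied answers are confirmed and the outcomes are separate.

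The SAP also does not show that any shared record exists. Copying is a fallback, and with 3 to 6 evenly spread pairs at ρ of 0.2 to 0.5 the simulated coverage is 94.5% to 94.8%, which is negligible. Its own example pairs two team types. If the types differ in mean pneumonia percentage, that unmodelled difference works against the correlation. With an assumed gap of 1.5 SD and ρ = 0.2, coverage is about 95.0% with 12 pairs and 95.6% with 24. Finally, the SAP does not say how standard errors are computed; ordinary ones are the natural reading of an unqualified linear regression. Its sensitivity list is open-ended, though it does not mention Trust.

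These points limit the size and keep the matter minor. They do not remove it: the plan allows for same-Trust pairs, treats their rows as independent without saying why, and gives no count from which to judge the effect.

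**Conclusion.** The point holds as a minor weakness in the analysis. If same-Trust pneumonia percentages are positively correlated, identical-answer rows make the planned 95% intervals too narrow. At 120 teams and ρ = 0.5 the loss runs from about half a percentage point of coverage (6 evenly spread pairs, 50/50 split) to about four points (10 pairs all in the smaller group of an 80/20 split). The pair count, the correlation, the split and the 120 teams are all assumptions.

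Two further readings go too far. A reader might infer that the copied rows can shift the intervals either way. With positive correlation they can only narrow them; intervals that are too wide need negative correlation, or same-Trust teams that answered differently. A reader might also infer that the effect is known to be slight, or known to be serious. The document settles neither, because a few evenly spread pairs hardly matter while pairs concentrated in a small exposure group do.

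**What to change.** In Statistical analyses, add that teams will be mapped to NHS Trusts from the hospital name in Survey Question #3 ("Please type the name of your hospital and select from the drop-down menu"), since no Trust identifier is described. Report the four regressions with standard errors clustered by Trust beside the planned ordinary regression, using a small-sample correction such as CR2 with Satterthwaite degrees of freedom. The uncorrected clustered form is not a good substitute: with no pairs up to 12 pairs at ρ = 0.5, it covered only 94.2% to 93.8% at an 80/20 split and 92.1% to 91.2% at 90/10. The CR2 form covered 94.3% to 95.5% in all 48 cases simulated (6,000 runs each, about ±0.6 points).

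Survey administration says "Completed survey responses were exported from Qualtrics to SPSS software for statistical analysis", so name the procedure that will produce these errors. If none is available, add to Sensitivity analysis a run with one row per confirmed shared survey, averaging the two teams' percentages. That covered 94.6% to 95.5%, but it deals only with shared surveys, not with same-Trust teams that replied separately, and it merges the percentages of what may be two team types. In either case, state the number of shared-answer records.

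The cost is a few lines of text, a Trust lookup, a little more analysis and somewhat wider intervals. At a 50/50 split, CR2 intervals are 0.2% wider when same-answer pairs are uncorrelated, and 2.5%, 5.0% and 10.0% wider with 6, 12 and 24 pairs at ρ = 0.5. Uneven splits cost more: with 6 to 12 uncorrelated pairs, 2% to 3% at 80/20 and 11% to 12% at 90/10, and up to 27% at 90/10 with 24 pairs at ρ = 0.5. This is why the clustered results are better placed beside the planned regression than in its stead. The one-row fallback is 1% to 9% wider.

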## **Sensitivity analysis**

Sensitivity analysis will be undertaken to understand how certain values contribute to the overall uncertainty of the model. For example, the impact of a lower-than-average response rate from a particular SCN region or the latest SSNAP annual data which includes data for the Covid-19 period compared to 2019 data (pre Covid-19).

## **Appendix**

Published electronic version of the survey “Dysphagia Screening, Assessment and Management in Acute Stroke” 2/9/2020.

